All randomized participants who underwent the surgical intervention (regardless of which technique was ultimately performed).

Protocol deviations will be prospectively classified as **major** (potentially affecting primary outcome validity) or **minor** (unlikely to affect outcomes) and documented in a deviation log.

SAP-3. BASELINE CHARACTERISTICS

Baseline characteristics will be summarized for the **ITT population** by treatment group:

Variable Type	Summary Statistic
Continuous, normally distributed	Mean ± Standard Deviation
Continuous, non-normal distribution	Median (Interquartile Range, IQR)
Categorical	n (%)

Normality of continuous variables will be assessed using both the **Kolmogorov-Smirnov test** and the **Shapiro-Wilk test**, complemented by visual inspection of Q-Q plots and histograms.

Variables to be summarized include: age, BMI at delivery, gestational age, parity, indication for cesarean section, type of anesthesia, skin incision type, uterine exteriorization status, pre-operative hemoglobin and hematocrit, and attending surgeon (anonymized).

No inferential statistics (p-values) will be calculated for baseline comparisons, as any imbalances in a randomized trial result from chance rather than systematic bias (CONSORT Statement 2010).

SAP-4. PRIMARY OUTCOME ANALYSIS

Outcomes:

1. **RMT** at 6–8 weeks and 6–7 months (continuous, mm)
2. **CSD prevalence** at 6–8 weeks and 6–7 months (binary)

SAP-4.1 RMT — Unadjusted Analysis

- **If normally distributed:** Independent samples **t-test** (or Welch's t-test if unequal variances)
- **If non-normally distributed: Mann-Whitney U test**

Reported statistics:

- Mean \pm SD (or Median [IQR]) per group
- Mean difference (MD) with 95% Confidence Interval
- Two-sided p-value (significance threshold: $\alpha = 0.05$)
- Effect size: Cohen's d (t-test) or rank-biserial correlation (Mann-Whitney)

SAP-4.2 RMT — Adjusted Analysis (Primary)

A **multiple linear regression model** will be constructed:

Dependent variable: RMT at 6–7 months

Independent variables:

- Treatment group (primary predictor)
- Age (continuous)
- BMI (continuous)
- Gestational age (continuous)
- Uterine exteriorization (yes/no)
- Surgeon experience level (senior/resident Year 4–5)
- Duration of labor before cesarean section (if applicable)
- Indication for cesarean section

Model assumptions verified:

- Linearity (partial regression plots)
- Homoscedasticity (Breusch-Pagan test)

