- PSTEV and PSTC: Mann-Whitney U (likely non-normal); median difference with 95% CI

SAP-6. ADVANCED ANALYTICAL METHODS

SAP-6.1 Clinical Predictive Model for CSD

A **clinical predictive model** for CSD formation will be developed using **Firth penalized logistic regression**, justified by the ratio of events to variables approaching the threshold defined by Peduzzi et al.

Model development:

- Variable selection: univariate screening ($p < 0.20$) + a priori clinical variables
- Stability: **Bootstrap validation (10,000 replications)**
- Optimal threshold: **Youden Index**
- Internal validation: **10-fold cross-validation** and **70/30 data partition**
- Performance: AUC, sensitivity, specificity, positive and negative predictive values

SAP-6.2 Mediation Analysis

The **mediating role of CSD at 6 weeks** on the relationship between hysterorrhaphy technique and RMT at 6 months will be assessed using the **counterfactual mediation framework (Imai et al.)**.

Estimated quantities:

- **ACME** (Average Causal Mediation Effect): indirect effect through CSD at 6 weeks
- **ADE** (Average Direct Effect): direct effect of technique on RMT
- **Total Effect** and **proportion mediated**

Method: Bootstrap with **10,000 replications**

Sensitivity analysis: Critical ρ (rho) analysis to quantify robustness to unmeasured confounders

SAP-6.3 Inter-Operator Homogeneity

Breslow-Day test for homogeneity of treatment effects across operators (surgeons), to assess whether results are consistent regardless of the individual performing the procedure.

SAP-6.4 Measurement Reproducibility

Inter-observer concordance will be evaluated by **double-blind reading (n = 30 randomly selected examinations)**:

- Continuous variables (RMT, AMT): **Intraclass Correlation Coefficient (ICC)**
- Categorical variables (CSD presence): **Cohen's Kappa**

Temporal concordance of RMT measurements (6 weeks vs. 6 months):

- **Lin's Concordance Correlation Coefficient**
- **Bland-Altman analysis** (mean difference and limits of agreement)

SAP-7. SUBGROUP ANALYSES

Pre-specified subgroup analyses for the primary outcome (RMT at 6–7 months):

Subgroup Factor	Categories	Statistical Test
BMI category	< 30 vs. 30–34.9 kg/m ²	Interaction term in regression
Gestational age	37–38+6 vs. ≥ 39 weeks	Interaction term
Indication for CS	Labor dystocia vs. Fetal indication vs. Maternal indication	Interaction term
Uterine exteriorization	Yes vs. No	Interaction term

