Type of cesarean section	Scheduled vs. Intrapartum	Interaction term
Surgeon category	Senior vs. Resident Year 4–5	Interaction term

Test for interaction: Likelihood ratio test comparing models with and without the interaction term.

All subgroup analyses are exploratory and hypothesis-generating. No correction for multiple comparisons is applied to subgroup analyses; results will not drive primary conclusions.

Results will be presented in **forest plots**.

SAP-8. SENSITIVITY ANALYSES

Analysis	Method
SA-1: Per-Protocol population	Repeat primary analysis in PP population
SA-2: Intraoperative complication exclusion	Exclude participants with major intraoperative events (corporeal hysterotomy, hysterotomy extension > 2 cm)
SA-3: Multiple imputation for missing RMT	MICE — 5 scenarios: observed data, LOCF, best case, worst case, 6-week status carry-forward
SA-4: Inverse Probability Weighting (IPW)	Adjust for informative loss to follow-up
SA-5: Binary threshold analysis	Proportion with RMT < 2.5 mm and RMT < 3.0 mm; Chi-square test
SA-6: Complete case analysis	For comparison with imputed results

SAP-9. MULTIPLICITY AND TYPE I ERROR CONTROL

- **Primary outcomes:** $\alpha = 0.05$, two-sided, for each co-primary endpoint (RMT and CSD prevalence at 6 weeks and 6 months)
- **Secondary outcomes:** Exploratory; **Holm-Bonferroni correction** applied to control family-wise error rate
- **Unmeasured confounders:** **E-value** calculated to quantify the minimum strength of an unmeasured confounder needed to explain away observed associations

SAP-10. MISSING DATA STRATEGY

Data Type	Strategy
Primary outcome (RMT at 6 months)	Five imputation scenarios (MICE)
Secondary continuous outcomes	Complete case + sensitivity with imputation if > 10% missing
Binary outcomes	Complete case analysis

Symptom questionnaires	Linear mixed model (full information maximum likelihood)
------------------------	--

Missing data mechanism assessed by **Little's MCAR test**.

Participants lost to follow-up compared to completers on key baseline variables; reasons for dropout documented and reported.

SAP-11. PRESENTATION OF RESULTS

Results reported in accordance with **CONSORT 2010** guidelines:

- **Table 1:** Baseline characteristics (ITT population) — no p-values
- **Figure 1:** CONSORT flow diagram
- **Table 2:** Primary and secondary outcomes with between-group comparisons
- **Table 3:** Subgroup analysis (forest plots)
- **Table 4:** Multivariate analysis results

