11. SAMPLE SIZE CALCULATION

The sample size was determined based on the primary outcome — **RMT at 6 months** — using the standard formula for comparison of two independent means:

$$n = \frac{2 \times (Z_{\alpha/2} + Z_{\beta})^2 \times \sigma^2}{\Delta^2}$$

Parameters:

- Two-sided significance level: $\alpha = 0.05$ ($Z_{\alpha/2} = 1.96$)
- Statistical power: 80% ($Z_{\beta} = 0.842$)
- Conservative standard deviation: **$\sigma = 3.5$ mm**
- Minimum clinically meaningful difference: **$\Delta = 1.3$ mm**

Base sample size: 114 participants per group

Adjustment for loss to follow-up:

Based on local postpartum follow-up data and published literature, a **30% loss to follow-up rate** was anticipated:

$$n_{adjusted} = \frac{114}{1 - 0.30} \approx 163 \text{ per group}$$

Total enrolled: 384 participants (192 per group)

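### The BMI and gestational-age interaction tests for RMT split two continuous modifiers into two classes; if the effect changes gradually this costs power, by an amount that depends on how large the interaction is

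*SAP*

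**What the plan says.** SAP-7 lists six subgroup factors for RMT at 6–7 months. Two of them are measured on a continuous scale but enter as two classes: BMI, "< 30 vs. 30–34.9 kg/m"², and gestational age, "37–38+6 vs. ≥ 39 weeks". The interaction test is a "Likelihood ratio test comparing models with and without the interaction term". Section 9 of the analysis plan inside the combined document repeats the same cuts and the same test.

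The primary adjusted model in SAP-4.2 handles the same variables differently: its covariate list has "BMI (continuous") and "Gestational age (continuous"). The matching list in section 6.1 of the combined document's analysis plan names both variables without stating their coding.

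Neither document gives a reason for the cut at 30 kg/m² or at 39 weeks, and neither plans an interaction with the continuous variable. No power is stated for any interaction, and no distribution is given for BMI or gestational age. Both documents label the subgroup analyses exploratory and keep them away from the primary conclusions.

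**The concern.** The plan accepts a linear BMI term and a linear gestational-age term in its most important model. It then drops that scale when it asks whether either variable changes the treatment effect. With the cut, women with BMI 22 and 29.9 count as the same, and women with 29.9 and 30.0 count as different. If the closure effect changes gradually with BMI or gestational age, the two-class term captures only part of that change.

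The trial is sized for a main effect, so its interaction tests start with little power. Avoidable loss makes it more likely that a real gradient is shown in the forest plot with a non-significant interaction and read as a consistent effect.

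**Working it through.** **1. The plan's own figure.** The documents give power only for the main effect, in the sample-size section (section 11) of the protocol: "Statistical power: 80"%, two-sided α = 0.05, SD 3.5 mm, difference 1.3 mm. The formula gives n = 2 × (1.96 + 0.842)² × 3.5² / 1.3² = 113.8, so 114, matching "Base sample size: 114 participants per group". Dividing by 0.70 gives 163. Nothing comparable exists for an interaction, so the rest needs assumptions.

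**2. Information kept by a cut.** With 1:1 allocation and a linear interaction, replacing modifier X by the indicator I(X ≥ c) multiplies the non-centrality of the test by ρ = corr(X, I). The information kept is ρ².

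Assumed distributions (not in the documents):
- BMI: normal, mean 27–31, SD 3–5, truncated below the eligibility limit of 35.
- Gestational age: normal, mean 38.5–40, SD 1–1.3, truncated to 37–42 weeks. The lower limit follows the eligibility criterion; 42 is assumed.

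| Modifier, cut | Share at or above cut | ρ | ρ² |
|---|---|---|---|
| BMI, 30 (mean 27, SD 3) | 0.16 | 0.65 | 0.43 |
| BMI, 30 (mean 29, SD 4) | 0.36 | 0.77 | 0.60 |
| BMI, 30 (mean 31, SD 3) | 0.59 | 0.82 | 0.67 |
| Gestational age, 39 (mean 40, SD 1) | 0.84 | 0.69 | 0.47 |
| Gestational age, 39 (mean 38.5, SD 1.3) | 0.40 | 0.82 | 0.68 |

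For a graded effect, the cut test on 2 × 114 = 228 women is therefore worth a continuous test on about 98 to 155 women (0.43 × 228 to 0.68 × 228).

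**3. Power loss at a fixed reference power.** If the continuous test has power P, then λ = z(P) + 1.96, and the cut test has power Φ(ρλ − 1.96).
- P = 80% (λ = 2.80): BMI falls to 45–63%, a loss of 17–35 points. Gestational age falls to 48–64%, a loss of 16–32 points.
- P = 50%: the loss is about 14–25 points.
- P = 30%: the loss is about 8–15 points.

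Wider assumptions at 80% (BMI mean down to 26, or gestational age uniform) give about 13–45 points.

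**4. Power loss at a fixed slope in a trial of this size.** λ = slope × SD(X) × √N / (2σ), with N = 228, σ = 3.5 mm, and BMI of mean 29 and SD 4 before truncation (3.52 after, ρ = 0.77). For slope 0.20, λ = 0.20 × 3.52 × 15.1 / 7 = 1.52. The 5th to 95th BMI percentiles are 22.3 and 33.8.

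| Slope (mm per kg/m²) | Change in effect, 5th–95th percentile | Continuous | Cut | Loss |
|---|---|---|---|---|
| 0.10 | 1.15 mm | 12% | 9% | 3 points |
| 0.15 | 1.7 mm | 21% | 14% | 6 points |
| 0.20 | 2.3 mm | 33% | 22% | 11 points |
| 0.30 | 3.5 mm | 62% | 42% | 20 points |
| 0.43 | 5.0 mm | 90% | 71% | 19 points |

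Simulated likelihood ratio tests for the last two slopes (4,000 runs) gave 62% versus 42% and 89% versus 70%. With no interaction both tests rejected about 5% of the time, so the gain is not bought with type I error.

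**5. Interaction size behind the 80% reference.** With 228 completers, 80% continuous power needs (1.96 + 0.842) × 2 × 3.5 / √228 = 1.3 mm per SD of the modifier. One SD of BMI would have to shift the treatment effect by the trial's whole target difference.

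**The case against.** **The size of the loss is not a property of this trial.** A reader might infer that these tests lose some 17–35 points of power outright. The documents do not support that: they state no interaction power, no modifier distribution and no expected interaction. When the effect changes across the BMI range by about the target difference (slope 0.10), both tests are nearly uninformative and the loss is about 3 points. This objection stands, and the size must be given conditionally. The fraction of information kept does not depend on the reference power, but it does depend on the assumed distributions. Truncated normality is least secure for gestational age, because scheduled and intrapartum cesareans are mixed.

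**The cuts are not median splits.** A reader might take the classes to be halves. They are fixed values and the class sizes are unknown.

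**Linearity is also an assumption.** The documents do not favour a graded effect over a threshold, and a step exactly at 30 kg/m² or 39 weeks would be better detected by the categories. This stands as a real limit. Against it, no reason is given for expecting a step there, and the plan already uses linear terms for both variables.

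**The analyses are exploratory.** This limits the consequence but does not remove the gain. A hypothesis-generating test is meant to find signals, and these tests are pre-specified and will be displayed.

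**It is late.** The SAP is dated 23 April 2026, study completion is given as 30 April 2026, and the principal investigator is unblinded. A change is therefore more than a wording edit if lock or unblinding has occurred.

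**Conclusion.** The point holds as a minor improvement. Both documents test effect modification by BMI and gestational age with two-class terms, although SAP-4.2 keeps both variables continuous, and no continuous interaction is planned. For a graded modification the cuts keep about 43–68% of the information under the stated assumptions. The loss is about 16–35 points at 80% continuous power, about 8–15 points at 30%, and a few points for small interactions. For a step at the cut the comparison reverses.

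A reader might also infer that the RMT result itself is weakened. It is not: RMT is analysed on its full scale, the primary model already uses continuous covariates, and no primary estimate, interval or conclusion depends on these tests. Nor would the change make the interaction tests well powered; for modest gradients they stay weak either way.

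**What to change.** In SAP-7, and in section 9 of the combined document's analysis plan, base the two tests on treatment × continuous BMI and treatment × continuous gestational age. Add each in turn to the SAP-4.2 model and use the likelihood ratio test with 1 df each. Report the change in adjusted mean difference per 5 kg/m² and per week, with 95% CI. Keep the existing classes as descriptive forest-plot rows, with the continuous-interaction p-value beside them. The other four factors are categorical and stay as they are.

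The test assumes roughly linear modification, so add a check by residual plot or a quadratic interaction term. SAP-4.2 already checks linearity, and this extends it.

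The cost is a few lines of text in each document, with no new data, patients or software. The change should be made before database lock and unblinding. After that, report it as a documented and justified deviation, as the SAP requires, alongside the categorical tests as planned. The analyses remain exploratory.

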12. MISSING DATA

Little's MCAR test to assess missing data mechanism.

Outcome	Strategy
RMT at 6 months	Five-scenario MICE (SA-3)
Secondary continuous	Complete case + MICE if > 10% missing
Binary outcomes	Complete case
Symptom questionnaires	Full information maximum likelihood (FIML) via mixed models

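### The rule for missing 6-month RMT is labelled MICE but lists scenarios that are not multiple imputation as written, none is named primary, and co-primary CSD is complete case only

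*SAP*

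**What the plan says.** **RMT at 6–7 months.** In the SAP, the SAP-10 entry for this outcome is "Five imputation scenarios (MICE", closed with a bracket and nothing more. In the combined document, section 12 of the SAP part has "Five-scenario MICE (SA-3", again closed with a bracket, which points to a row in the table of sensitivity analyses. Both documents define SA-3 by the same five items; in the SAP they read "MICE — 5 scenarios: observed data, LOCF, best case, worst case, 6-week status carry-forward". Neither document gives an imputation model, auxiliary variables, a number of imputations or a pooling rule. The combined document's software section names the mice package.

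**CSD.** Prevalence at both visits is a binary co-primary endpoint. The only SAP-10 rule for binary outcomes is "Complete case analysis", and CSD is not excepted.

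**Other relevant provisions.** SA-4 is inverse probability weighting (IPW) for informative loss to follow-up. SA-6 is a complete-case analysis, listed for comparison with the imputed results. SAP-5.4 is a secondary linear mixed model of RMT at both visits with a treatment-by-time term. Little's test and a comparison of women lost with completers are also planned.

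**Population and expected loss.** Section 4.1 of the SAP part of the combined document makes the primary population all 384 women as allocated. Protocol section 5.3 lists loss to follow-up among the reasons for exclusion after randomization. Protocol section 11 anticipates a "30% loss to follow-up rate".

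**The concern.** SAP-4.2 names the primary regression for RMT but not the data it uses for women without a 6-month scan. SAP-10 answers with SA-3, a sensitivity analysis that offers several answers and ranks none. If nothing is imputed, the regression can use only women who were scanned, and the result would be a complete-case estimate carrying the ITT label. If the 6-week value is carried forward, the result mixes the effects at two times, although the primary objective in protocol section 3.1 asks whether the effect is stable over time.

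The SAP's stated purpose is to prevent decisions made after the data are seen. Protocol sections 7.3 and 13 say that the principal investigator is unblinded and holds both clinical and allocation data. An unranked list of scenarios for the primary outcome leaves that kind of decision open.

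**Working it through.** **1. The plan's own sample size.** Inputs from protocol section 11: "Two-sided significance level" 0.05 (Z = 1.96); "Statistical power: 80"% (Z = 0.842); "Conservative standard deviation" 3.5 mm; difference 1.3 mm.

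- n = 2 × (1.96 + 0.842)² × 3.5² / 1.3² = 2 × 7.851 × 12.25 / 1.69 = 113.8, so 114 per group. This matches.
- 114 / (1 − 0.30) = 162.9, so 163 per group. This matches.
- Enrolment is stated as 192 per group.

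**2. What 30% loss leaves.**

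- Missing: 192 × 0.30 = 57.6, about 58 per group (384 × 0.30 = 115.2, about 115 in all).
- Remaining: 192 × 0.70 = 134.4, about 134 per group.
- Standard error = 3.5 × √(2/134) = 0.428 mm; 1.3 / 0.428 − 1.96 = 1.08; power about 86%.

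**3. The five SA-3 items, read literally.**

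| Item | What it does for 6-month RMT |
|---|---|
| Observed data | Appears to be the complete-case analysis, already SA-6 |
| LOCF | Fills with the 6–8-week value, the only earlier scan |
| 6-week carry-forward | The same rule as LOCF |
| Best case | No value in mm defined |
| Worst case | No value in mm defined |

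This leaves four distinct items, one of which repeats SA-6. Carry-forward cannot fill a woman who missed both scans, because no earlier scar measurement exists.

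**4. Size of the carry-forward bias.** Assume that dropout is completely random, that 30% are missing in each arm, and that every dropout had the 6–8-week scan. Then

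estimate = 0.7 × (6-month effect) + 0.3 × (6-week effect),

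so bias = 0.3 × (6-week effect − 6-month effect). The documents give no 6-week effect, so a range is shown for a true 6-month effect of 1.3 mm:

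| 6-week effect (assumed) | Estimate |
|---|---|
| 0 mm | 0.91 + 0.00 = 0.91 mm |
| 0.5 mm | 0.91 + 0.15 = 1.06 mm |
| 1.3 mm | 0.91 + 0.39 = 1.30 mm |
| 2.0 mm | 0.91 + 0.60 = 1.51 mm |

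**5. Dropout related to the early scan.** A simulation used 2,000 replicates, 192 per group, SD 3.5 mm, an assumed correlation of 0.6 between visits, about 30% missing, the 6-week scan always observed, and a true effect of 1.3 mm at both visits. In a deliberately strong case, dropout depended on 6-week RMT in opposite directions in the two arms. Mean estimates were 0.32 mm for complete case and 1.74 mm for LOCF. Regression imputation by arm, which gives the point estimate of multiple imputation or of an unstructured likelihood model, gave 1.30 mm. IPW with the known dropout model also gave 1.30 mm. This shows direction only; it does not predict the trial's result.

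**6. CSD.** With 30% missing per arm, the risk difference is 0.7 × (observed difference) + 0.3 × (difference among the missing). The last difference can lie anywhere from −1 to 1, so the missing women can contribute up to 0.30 either way.

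**The case against.** A reader might infer that 30% missing data has no valid handling anywhere in the plan. The documents do not support that. IPW (SA-4) can be valid for RMT under missing at random. So can the SAP-5.4 mixed model, which keeps women who have only the early scan and yields a 6-month contrast. Complete-case regression is itself unbiased if dropout is completely random, or depends only on treatment and the SAP-4.2 covariates in a correctly specified model.

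These points stand, with limits. SA-4 is only a sensitivity analysis, states no weight model and does not say that it covers CSD. SAP-5.4 is secondary, lists no adjustment covariates and is not linked to the missing-data rule for RMT; that section uses mixed models only for symptom questionnaires. The SAP-4.2 covariates do not include the 6–8-week scan, so dropout related to early scar findings is not covered by the complete-case argument.

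It can also be said that MICE is really intended. SA-3 is titled multiple imputation, SA-6 is set against imputed results, the mice package is named, and the combined document plans MICE for secondary continuous outcomes with more than 10% missing. Observed data might mean imputation from observed data. That is possible, so the repetition of SA-6 is a likely reading, not a certainty. Even on the generous reading, no model, number of imputations or pooling rule is given, and no scenario is primary.

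Two further inferences fail. Carry-forward does not always dilute the effect: it inflates it if the early effect is larger and leaves it unchanged if the effects are equal. The trial is not short of power at the expected loss, since 134 per group exceeds the 114 required.

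**Conclusion.** The point holds in this form: no valid missing-data method is pre-specified for the primary 6-month RMT estimate, and co-primary CSD has no explicit provision beyond complete case. MICE is named but not specified, and the listed scenarios overlap, are partly undefined and are unranked. The ITT definition and the exclusion for loss to follow-up conflict.

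The consequence is possible bias and an undefined primary estimate for about 58 women per group, while power stays at about 86%. Under completely random dropout, with every dropout scanned at 6–8 weeks, carry-forward shifts the RMT difference by 0.3 mm for each 1 mm gap between the 6-week and 6-month effects, in either direction. The documents do not say when the 30% loss occurs, so the number of dropouts with an early scan is unknown. That limits both the carry-forward figures and how much any imputation can recover.

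**What to change.** Before unblinded analysis, and as a documented SAP change:

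- Name one primary missing-data method for RMT and CSD at 6–7 months. One option is MICE by arm, with 6–8-week RMT and CSD, adjacent myometrial thickness and the SAP-4.2 covariates in the imputation model. Analyse with the SAP-4.2 and SAP-4.3 models and pool by Rubin's rules. State the number of imputations.
- For RMT, promoting the two-visit likelihood model of SAP-5.4, with the covariates added, is an acceptable alternative and a smaller change. CSD would still need its own rule.
- Keep SA-4, with its weight model written out, and SA-6 as sensitivity analyses.
- Remove the duplicate scenarios, and replace LOCF and best and worst case with a delta-adjusted analysis by arm.
- Reconcile protocol section 5.3 with the ITT definition, so that it is clear how women lost to follow-up enter the primary analysis.
- Make the same change in both SAP texts.

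The cost is extra analysis code, using a package already named, and a documented amendment. The confidence interval may differ slightly from the complete-case one. No new data are needed.

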10. DATA COLLECTION AND FOLLOW-UP SCHEDULE

Time Point	Assessment
Preoperative	Eligibility verification, informed consent, baseline NFS (CBC), demographics
Intraoperative	Randomization, surgical parameters, hysterorrhaphy duration, operative time, blood loss, complications
Postoperative Day 1	NFS (hemoglobin), vital signs, wound assessment
Discharge	Wound assessment, clinical evaluation, length of stay
6–8 Weeks postpartum	TVUS (RMT, CSD assessment), AMT, RM, clinical examination, standardized symptom questionnaire
6–7 Months postpartum	TVUS (RMT, CSD — PRIMARY ENDPOINT) , AMT, RM, CSD dimensions, volume, standardized symptom questionnaire

Ultrasonographic Examination Protocol

All TVUS examinations are performed:

- By a **dedicated, trained ultrasonographer per center, blinded to group allocation**
- Using **Samsung HS40 ultrasound system with EVN4-9 endovaginal probe (4–9 MHz)**
- With **standardized imaging parameters**

- With the **bladder empty**
- **Preferably in the follicular phase (Day 7–14 of the menstrual cycle)** to optimize defect visualization
- In the **mid-sagittal plane**: depth, length, and RMT measured; width measured in transverse plane
- **RMT measured perpendicular to the serosa at the thinnest point of the scar**

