3. PRIMARY AND CO-PRIMARY ENDPOINTS

Endpoint	Time Points	Variable Type
----------	-------------	---------------

Residual Myometrial Thickness (RMT)	6–8 weeks AND 6–7 months	Continuous (mm)
CSD Prevalence (indentation \geq 2 mm, Jordan 2019)	6–8 weeks AND 6–7 months	Binary

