11. MULTIPLICITY CONTROL

- Primary outcomes: $\alpha = 0.05$, two-sided
- Secondary outcomes: **Holm-Bonferroni correction**
- Unmeasured confounders: **E-value** reported for primary associations

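### Four primary tests each get a two-sided 0.05 with no decision rule, so type I error is uncontrolled if any one result can carry a primary claim (18.5% if independent, about 10–16% at assumed correlations of 0.9 down to 0.5)

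*SAP*

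**What the plan says.** SAP-4 of the standalone SAP lists two primary outcomes: RMT "at 6–8 weeks and 6–7 months (continuous, mm") and CSD prevalence "at 6–8 weeks and 6–7 months (binary"). Protocol section 9.1 and section 3 of the SAP embedded in the combined document do the same, the latter giving both endpoints the time points "6–8 weeks AND 6–7 months".

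For error control, SAP-9 assigns 0.05, "two-sided, for each co-primary endpoint (RMT and CSD prevalence at 6 weeks and 6 months"). Section 11 of the embedded SAP says only "Primary outcomes: $\alpha = 0.05$, two-sided". In SAP-9, Holm-Bonferroni is "applied to control family-wise error rate" for secondary outcomes, which the same line calls exploratory. Neither plan states a hierarchy, gatekeeping, an alpha split or an all-must-succeed rule for the primary tests.

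Other places narrow the focus:

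- Protocol section 11: "The sample size was determined based on the primary outcome", identified there as RMT at 6 months.
- SAP-4.2 labels its adjusted model primary and fits it to RMT at 6–7 months.
- SAP-7 and SAP-10 refer to RMT at that visit as the primary outcome.
- The visit schedule in protocol section 10 marks the 6–7-month visit "TVUS (RMT, CSD — PRIMARY ENDPOINT"), which names both outcomes.

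**The concern.** A plan with several primary tests has to say what counts as a positive trial. This one alternates between one primary outcome, two at 6–7 months, and four, and attaches no decision rule to any of them. With 0.05 for each test, a single nominal p-value below 0.05 among four could be reported as a positive primary result, and the choice of which to emphasise could be made after the results are known. The confirmatory tests also have less protection than the exploratory ones, in a section whose title promises type I error control.

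**Working it through.** **Inputs from the documents.** Four primary tests at two-sided 0.05 each (SAP-4, SAP-9). Sample size at two-sided 0.05 with 80% power, SD 3.5 mm, difference 1.3 mm, 30% loss, 192 enrolled per group (protocol section 11). **Assumed:** the correlations among the four test statistics, which the documents do not give; 0 to 0.9 is examined.

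**1. The plan's own figure.** n = 2 × (1.96 + 0.842)² × 3.5² / 1.3² = 113.8, so 114 per group. With 30% loss, 114 / 0.70 = 162.9, so 163. Both reproduce. The calculation spends the whole 0.05 on RMT at 6 months and makes no allowance for three further primary tests.

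**2. Independent tests.** 1 − 0.95⁴ = 0.1855, or 18.5%. Whatever the correlation, the bound is 4 × 0.05 = 20%. For the two 6–7-month tests alone, 1 − 0.95² = 9.75%.

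**3. Correlated tests.** Four standard normal statistics were simulated with no true effect. The correlation is r between times and r between endpoints, and r² when both differ. Simulated values are good to about 0.1 percentage point.

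| r (assumed) | At least one of four below 0.05 | At least one of the two 6–7-month tests | All four below 0.05 |
|---|---|---|---|
| 0 | 18.5% | 9.75% | < 0.01% |
| 0.5 | 16.1% | 9.1% | 0.1% |
| 0.7 | 13.7% | 8.3% | 0.4% |
| 0.8 | 12.0% | 7.8% | 0.8% |
| 0.9 | 9.8% | 7.0% | 1.7% |

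One common correlation among all four tests gives slightly lower figures for the first column: 15.6% at 0.5, 13.0% at 0.7, 11.4% at 0.8 and 9.3% at 0.9.

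The last column assumes no effect on any endpoint. More generally, a rule requiring all four to succeed has error of at most 5%, because any truly null endpoint must itself pass at 0.05.

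**4. What control would cost.** Evaluable per group at 30% loss: 192 × 0.70 = 134.4, so about 134. The standard error of the RMT difference is 3.5 × √(2/134) = 0.428, and 1.3 / 0.428 = 3.04.

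- At 0.05 (first step of a fixed sequence): Φ(3.04 − 1.96) = 86% power.
- At 0.05 / 4 = 0.0125 (equal Bonferroni): Φ(3.04 − 2.50) = about 71% power. Restoring 80% would take 162 evaluable per group, or 162 / 0.70 = 231.4, so 232 enrolled, against 192.

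**The case against.** The strongest reply is that co-primary can mean all endpoints must be significant, and then no alpha adjustment is needed. That is true, but neither plan says so, and giving the level to each endpoint points towards separate claims. Even on that reading a rule is missing, and the sample size addresses only RMT at 6 months, so the power to succeed on all four is unassessed.

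A second reply is that the endpoints are strongly related: the same women are measured twice, and RMT is measured from the base of the niche when one is present. Independence is therefore unlikely, and 18.5% is an upper-end figure. This stands as a limit on the size, but even at 0.9 the rate is about 9–10%.

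Third, if the plan's emphasis on RMT at 6–7 months were binding, the error for that one claim would be 5%. The emphasis is never turned into a testing rule, however.

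Three stronger readings are tempting, and the documents do not support them:

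- That this trial's false-positive rate simply is 18.5%, or that the plan promises 5% overall and breaks the promise. The figure depends on any one result sufficing and on assumed correlations, and the documents state 0.05 per endpoint without claiming a family-wise rate.
- That the documents already make RMT at 6–7 months the sole primary. The visit schedule names RMT and CSD together, protocol sections 3.1 and 9.1 make both primary at both times, and section 6.1 of the embedded SAP gives its adjusted RMT model no time point.
- That the documents dictate a full testing order. They support RMT at 6–7 months first and 6–7 months as the main visit. They do not rank CSD at 6–7 months against RMT at 6–8 weeks.

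**Conclusion.** The point holds in a conditional form. As written, SAP-9 does not control type I error over the primary claims and does not define a positive trial. If any single success counts, family-wise error is 18.5% under independence and about 10–16% at assumed correlations of 0.9 down to 0.5. If only the two 6–7-month tests count, it is about 7–10%. None of the correlations examined brings it down to 5% while any one test can carry the claim. An all-must-succeed rule would hold it at 5% or less, but the plan does not state one.

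Timing makes this pressing. The standalone SAP is dated 23 April 2026, a week before the stated study completion date, and the principal investigator holds both clinical and allocation data. A rule recorded before unblinded results are seen is credible; a later one is not.

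**What to change.** Before the database is locked and the data unblinded, write a fixed sequence into the plan. Each step is tested at two-sided 0.05 only if every earlier step succeeded:

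1. RMT at 6–7 months, using the adjusted model of SAP-4.2. This endpoint comes first because SAP-4.2, SAP-7, SAP-10 and the sample size already single it out.
2. CSD prevalence at 6–7 months, with one named test. The unadjusted chi-square or Fisher test of SAP-4.3 is a reasonable choice, because the logistic model there selects covariates by p < 0.20 screening. Unless one test is fixed, this step does not hold at 0.05.
3. RMT and then CSD at 6–8 weeks, again with one named test each.

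Once a step fails, report the remaining endpoints as estimates with 95% confidence intervals and make no confirmatory claim. State that the order after the first step is a choice, and record that it was made before unblinded results were seen. If the sponsor instead intends all four to be required, the plan should say so and assess the joint power.

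The places to amend are SAP-4, SAP-9, sections 3 and 11 of the embedded SAP, and protocol sections 3.1 and 9.1. Protocol section 12 requires ethics review of amendments, so this is more than an edit to the SAP.

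The cost is that CSD cannot be claimed as confirmatory if RMT at 6–7 months is not significant, which lowers its standing relative to the joint objective in protocol section 3.1. Power for RMT at 6–7 months is unchanged, and no further participants are needed.
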